Allogeneic HB-adMSCs to provide immune support against COVID-19.

Study Endpoints

Primary endpoints:

- Incidence of hospitalization for COVID-19.
- Incidence of symptoms associated with COVID-19.

Secondary endpoints:

- Absence of upper/lower respiratory infections (with hospitalization criteria) up to 3 months post infusions.
- Change from baseline in leukocyte differential
- Change from baseline in C-Reactive Protein
- Change from baseline in TNF-alpha
- Change from baseline in IL-6
- Change from baseline in IL-10
- Clinically significant changes in laboratory values, vital signs, weight, X-rays, ECG, and physical examination results.
- Incidence of AEs (AEs) and serious AEs (SAEs) related to the drug

Investigational Plan

This Phase 2, randomized, double-blind, single center, efficacy and safety study, is designed to evaluate allogeneic HB-adMSCs to provide immune support against COVID-19 in subjects classified as high risk. 'High risk', according to CDC at the time of protocol development, includes subjects age 65 or older, as well as subjects in high exposure environments such as healthcare professionals and law enforcement, or individuals with preexisting conditions, including but not limited to cardiopathies, diabetes mellitus, cancer, COPD, asthma or any other systemic autoimmune disease. The study will have 4 arms:

Arm 1 (allogeneic HB-adMSCs 200MM)

Subjects assigned to this arm will receive HB-adMSCs during the whole duration of the study.

Arm 2 (allogeneic HB-adMSCs 100MM)

Subjects assigned to this arm will receive HB-adMSCs during the whole duration of the study.

Arm 3 (allogeneic HB-adMSCs 50MM)

Subjects assigned to this arm will receive HB-adMSCs during the whole duration of the study.

Arm 4 (Placebo)

Subjects assigned to this arm will receive placebo injections throughout the entire duration of the study.

The screening period, up to 45 days long for each patient, will be used to assess eligibility. At baseline (Week 0), approximately 53 patients who are eligible will be randomized in a 3:1 ratio

Allogeneic HB-adMSCs to provide immune support against COVID-19.

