Allogeneic HB-adMSCs to provide immune support against COVID-19.

- The patient develops a severe allergic reaction that occurs following investigational product administration.

A patient may voluntarily withdraw or be withdrawn from the study at any time for reasons including, but not limited to, the following:

- Patient withdrawal of consent: At any time, a patient's participation in the study may terminate at his/her request. The specific reason for patient withdrawal will be noted on the case report form (CRF).
- Lost to follow-up: The patient stops coming for visits, and study personnel is unable to contact the patient after repeated attempts (e.g., mail, or email).
- This study may be terminated at the discretion of the Sponsor or any regulatory agency.

If a patient's infusions are discontinued at any point during the trial and the patient maintains consent to contribute additional outcome information, the patient should continue to be followed through Week 26 for all safety and efficacy assessments. Investigators will be trained about the importance of retention and steps to prevent missing data.

The date and reason for withdrawal are to be documented in the CRF. The study site must immediately notify the medical monitor. The patients who withdraw prematurely must attend an early discontinuation visit if possible, at which time they will complete all assessments described in Table 2 under the Week 24 visit.

In the event that a patient discontinues prematurely from the study due to an Adverse Event (AE) or serious AE, the event will be followed until it resolves (returns to normal or baseline values) or stabilizes, or until it is judged by the Investigator to be no longer clinically significant. Once a patient is withdrawn from the study, the patient may not re-enter the study. If the subject develops symptoms associated with COVID-19 during the conduct of this study, they will be asked to consult their personal physician and be tested for COVID-19, and to self-quarantine for at least 14 days. Quarantine must occur while waiting for COVID-19 test results. Once asymptomatic, subject may resume site visits. If the test results are positive, the subject will be asked to quarantine and may continue to receive infusions at the quarantine site. If the subject develops severe symptoms (i.e., shortness of breath/difficulty breathing) they should go to the ER instead of personal physician.

Treatments

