Allogeneic HB-adMSCs to provide immune support against COVID-19.

Each patient will be allocated a unique subject number at screening and will retain this number throughout the study. The first 4 patients (1 for each group) will receive their first infusions on weeks 0 and 2. Upon successful completion of infusion 2 for the first 4 patients, the DSMB will meet at least 48hrs after the last second infusion, to review safety. If permitted by DSMB, the rest of the patients can receive their infusions as long as all inclusion criteria have been met and none exclusion criteria is.

The Investigational Product is to be administered to eligible, enrolled patients by intravenous infusion at a dose that will depend on the group they have been randomized to:

- Group 1→2 x10⁸ cells at weeks 0, 2, 6, 10 and 14.
- Group 2→1 x10⁸ cells at weeks 0, 2, 6, 10 and 14.
- Group 3→5 x10⁷ cells at weeks 0, 2, 6, 10 and 14.
- Group 4→Placebo infusions at weeks 0, 2, 6, 10 and 14.

Every effort should be made to adhere to the dosing schedule. However, a scheduled infusion should not be administered if a patient has an ongoing AE that, in the Investigator's opinion, warrants holding the infusion.

Blinding

Blinding for Dose Administration

All patients, investigators, mixer, and site staff will be blinded to treatment assigned.

Amber bags covering the saline will be used for product infusion. Only subject ID, DOB and expiration date will be on the bag label, to ensure proper distribution. Mixer will inject product into the bag before handing off to the clinical team.

Blinding for Clinical Evaluators

To minimize assessment bias, clinical evaluators (data analysts and physicians) will be trained on how to maintain blinding to treatment as best as possible. "Best as possible" means that blinding will be maintained unless an adverse event occurs that requires unblinding the physician, which is determined by the medical monitor or DSMB. Training includes review of the process of blinding, describing who will be responsible for assigning product for the appropriate group, labels that will be used to identify subjects but not treatment group, and the process that should be followed if an adverse event occurs, triggering review by medical monitor and/or DSMB.

Planned Unblinding

Allogeneic HB-adMSCs to provide immune support against COVID-19.

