Unblinding of patient and researcher will occur in the case of adverse event suspected to be related to the investigational product, per the medical monitor and DSMB.

Regulatory authorities and/or the IRB may request the unblinding of data from one or more patients at any time.

Prior and concomitant conditions

The investigators should document all prior significant medical history. Additional conditions present at the time when informed consent is given and up to the time of first infusion (Week 0) are to be regarded as concomitant conditions. Illnesses first occurring or detected during the study and/or worsening of a concomitant condition during the study should be documented as AEs in the CRF.

Prior and concomitant medications

All medications, including over-the-counter treatments and preventative vaccines taken by the patient during the study, including those treatments initiated prior to the start of the study, must be recorded in the CRF. The entry must include the dose, regimen, route, indication, and dates of use.

Study Procedures

Table 2 outlines the timing of procedures, and assessments to be performed throughout the study.

Table 2. Schedule of Assessments

Visit Number	1	2	3	4	5	6	7	8	9
Weeks	N/A	Week 0	Week 2	Week 6	Week 10	Week 14	Week 18	Week 22	Week 26
Visit Name	Screening (Phone call)	Infusion-1 /Baseline	Infusion 2	Infusion 3	Infusion 4	Infusion 5	Follow Up	Follow Up	EOS
Window Period	Up to 45 days	±4 days	±4 days	±4 days	±4 days	±4 days	±4 days	±3 days	±3 days
STUDY PROCEDURES									
Informed Consent	X	X							
Inclusion and Exclusion Criteria	X	X							
Pre-infusion assessment		X	X	X	X	X			
Review of Medical History	X	X	X	X	X	X	X	X	X
Concomitant Medication Review	X	X	X	X	X	X	X	X	X

Allogeneic HB-adMSCs to provide immune support against COVID-19.

Vital Signs		X	X	X	X	X	X	X	X
Weight and Height ¹		X	X	X	X	X	X	X	X
Physical Examination		X	X	X	X	X	X	X	X
SF-36 Questionnaire		X	X	X	X	X	X	X	X
PHQ-9		X	X	X	X	X	X	X	X
Rapid antibody COVID-19		X							X
CBC with differential		X		X		X			X
Chemistry		X		X		X			X
Coagulation Panel		X		X		X			X
CRP		X		X		X			X
IL-6		X		X		X			X
IL-10		X		X		X			X
TNF alpha		X		X		X			X
HB-adMSCs Administration		X	X	X	X	X			
24-hour telephone encounter		X	X	X	X	X			
Adverse Event Monitoring		X	X	X	X	X	X	X	X
1. Height will only be measured at baseline									

Informed Consent (ICF)

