- results in persistent or significant disability or incapacity
- Important Medical Events (IME): those events that may not result in death, be immediately life threatening, or require hospitalization. They may be considered a SAE when, based upon medical judgement, they may jeopardize the subject and may require intervention to prevent one of the other serious outcomes noted above. For example, drug overdose or abuse, a seizure that did not result in in-patient hospitalization, or intensive treatment of bronchospasm in an emergency department would typically be considered serious. (FDA, 21CFR312.32; ICH E2A and ICH E6)

All SAEs must be reported to Hope Biosciences immediately after the Investigator becomes aware of the event, along with a determination as to whether it is associated with the study drug. Patients will be instructed to report AEs at each study visit. All AEs are to be followed until resolution or until a stable clinical endpoint is reached.

Each AE is to be documented in the CRF with reference to onset date, duration, frequency, severity, relationship to study drug, treatment of event, and outcome. Furthermore, each AE is to be classified as being serious or non-serious. Changes in AEs and resolution dates are to be documented in the CRF.

For the purposes of this study, the period of observation for collection of AEs extends from the time the patient gives informed consent through Week 26 (or early discontinuation visit). Follow-up of the AE is required until the event resolves or stabilizes at a level acceptable to the Investigator.

Intensity of Adverse Event

The intensity of the AE will be judged based on the following:

- Mild: Awareness of sign(s) or symptom(s) which is/are easily tolerated
- Moderate: Enough discomfort to cause interference with usual activity
- Severe: Incapacitating or causing inability to work or to perform usual activities

Causal Relationship of Adverse Events

Medical judgement will be used to determine the relationship, considering all relevant factors, including pattern of reaction, temporal relationship, de-challenge and confounding factors such as concomitant medication, concomitant disease and relevant history. Assessment of causal relationship will be recorded in the CRF.

- **Definitely Related:** The adverse event is clearly related to the investigational product –

Allogeneic HB-adMSCs to provide immune support against COVID-19.

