i.e. an event that follows a reasonable temporal sequence from administration of the study intervention, follows a known or expected response pattern to the suspected intervention, that is confirmed by improvement on stopping and reappearance of the event on repeated exposure and that could not be reasonably explained by the known characteristics of the subject's clinical state.

- **Possibly Related:** An adverse event that follows a reasonable temporal sequence from administration of the study intervention follows a known or expected response pattern to the suspected intervention, but that could readily have been produced by a number of other factors.
- **Not Related:** The adverse event is clearly not related to the investigational product. - i.e. another cause of the event is most plausible; and/or a clinically plausible temporal sequence is inconsistent with the onset of the event and the study intervention and/or a causal relationship is considered biologically implausible.

Investigator Reporting: Notifying the Study Sponsor

Any study-related unanticipated problem posing risk to subjects or others, and any type of serious adverse event, will be reported to Hope Biosciences (Sponsor) by telephone within 24 hours of the event. To report such events, a Serious Adverse Event (SAE) form will be completed by the investigator and electronically faxed to the sponsor within 24 hours to [contact]. The investigator will keep a copy of this SAE form on file at the study site.

Within the following 48 hours, the investigator will provide further information on the Serious Adverse Event or unanticipated problem in the form of a written narrative. This should include a copy of the completed Serious Adverse Event form, and any other diagnostic information that will assist the understanding of the event. Significant new information on ongoing Serious Adverse Events should be provided promptly to Hope Biosciences.

Routine Study Close-out

The study will end when Hope Biosciences has obtained all data necessary to complete its studies of the investigational product. Standard procedures may include, but is not limited to, review of regulatory documents, collection of completed case report forms, reconciliation of study records, removal or destruction of ancillary study supplies, and informing the Investigator of remaining obligations (e.g., record retention, final report submission to the IRB, financial disclosure updates, etc.).

Infusion Stopping Rules

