Subjects may benefit from their participation in the study by experiencing an overall feeling of well-being. Subjects enrolled in the study will be contributing to the advancement of science and to future investigations regarding stem cells and possible therapeutic applications, including treatment and prevention of respiratory diseases, specifically COVID-19.

Statistical Analysis

Determination of Sample Size

Sample size calculation was determined based upon the number of patients currently banked at our facility and those who are already registered to bank. Sample size for this study is not to exceed 53 patients.

Null hypothesis- Efficacy

Treatment with HB-adMSCs does not cause changes in primary and secondary endpoints (listed below) for providing immune support against Coronavirus Disease.

Alternative hypothesis-Efficacy

The alternative hypothesis for this study is that HB-adMSCs treatment does result in changes from baseline values of primary and secondary endpoints in patients.

Null hypothesis-Safety

Treatment with HB-adMSCs results in adverse or serious adverse events and/or detrimental changes in laboratory values, vital signs, weight, X-rays, ECG, or physical examination determined to be related to the study drug.

Alternative hypothesis-Safety

HB-adMSCs treatment for COVID-19 does not result in adverse or serious adverse events and/or detrimental changes in laboratory values, vital signs, weight, X-rays, ECG, or physical examination determined to be related to the study drug.

Endpoints

The endpoints measured in this study are safety and clinical efficacy.

Safety is assessed by incidence of adverse and serious adverse events, incidence of specific adverse events including serious infections, infusion-related reactions, hepatotoxicity, heart failure, and cytopenia. Clinically significant changes in laboratory values, vital signs, weight, and physical examination results will also be measured.

Allogeneic HB-adMSCs to provide immune support against COVID-19.

Clinical efficacy is assessed by primary and secondary endpoints. Primary endpoints include incidence of hospitalization for COVID-19, incidence of symptoms associated with COVID-19, and severity of symptoms associated with COVID-19. Secondary endpoints include absence of upper/lower respiratory tract infections, change from baseline in inflammation, SF-36 and PHQ9 questionnaires.

Analysis Population

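### The protocol gives two conflicting unblinding rules; the broader one has no severity or need test, and the SAP has no rule for code breaks

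*Protocol*

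**What the plan says.** Two parts of the protocol's Blinding section govern the same act.

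- **Blinding for Clinical Evaluators:** "blinding will be maintained unless an adverse event occurs that requires unblinding the physician, which is determined by the medical monitor or DSMB". The participant is not mentioned.
- **Planned Unblinding:** "Unblinding of patient and researcher will occur in the case of adverse event suspected to be related to the investigational product". The same sentence adds a gate: the event must be "suspected to be related to the investigational product, per the medical monitor and DSMB".

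The Randomization section adds that only the randomizer will know the unblinded information.

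The adverse-event sections define the terms on which the trigger depends. The lowest intensity is "Mild: Awareness of sign(s) or symptom(s) which is/are easily tolerated". The lowest positive relatedness category, Possibly Related, includes an event that fits the timing and expected pattern "but that could readily have been produced by a number of other factors".

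SAP section 4 defines the efficacy set as all randomized participants who received all five infusions, analysed as randomized. Neither that section nor any other part of the SAP says how a participant whose code was broken is to be handled.

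**The concern.** Site staff cannot follow both rules. A participant with a mild reaction that is judged possibly related stays blinded under one and is told the assignment under the other.

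The broader rule matters for the analysis because it reaches both the participant and the researcher while outcomes are still accruing. The symptom co-primary endpoint (fever, cough, shortness of breath) depends in part on what the participant reports and whether he or she seeks testing. The SF-36 is completed by the participant at every in-person visit. At this single site the investigator or sub-investigator performs the physical examinations, so an unblinded researcher may also be an assessor. No blinded adjudication of symptoms is described. A blind that has been broken cannot be restored, and the SAP offers no way to judge afterwards what the breaks did to the result.

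**Working it through.** The plan has no figure of its own to reproduce. It states no related-event rate, unblinding rate, symptom rate, effect size or power, and the sample size comes from the number of banked patients. The check is therefore mainly of the text, with arithmetic to show scale.

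**1. The two rules side by side**

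- Trigger: an event that requires unblinding (Clinical Evaluators), against suspected relatedness (Planned Unblinding).
- Who learns the code: the physician, against patient and researcher.
- Who decides: medical monitor *or* DSMB, against medical monitor *and* DSMB.

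They differ on all three counts.

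**2. The least event that meets the broader trigger.** No intensity is excluded, so a mild event qualifies. No relatedness category above Not Related is excluded, so a possibly related event qualifies. The two bodies must agree, but the only test they are given is suspected relatedness.

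**3. Who remains in the efficacy analysis.** An unblinded participant who completes all five infusions stays in. One who stops earlier does not. The protocol's statement that "the patient should continue to be followed through Week 26 for all safety and efficacy assessments" concerns people whose infusions were discontinued, so it does not bring them into the efficacy set.

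**4. Outcome time left after a break.** Infusions run from Week 0 to Week 14, and outcomes are collected to Week 26. After infusion 1: 26 − 0 = 26 weeks. After infusion 5: 26 − 14 = 12 weeks.

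**5. Split between arms.** Inputs: "approximately 53 patients who are eligible will be randomized in a 3:1 ratio" (Investigational Plan) and "Sample size for this study is not to exceed 53 patients" (Determination of Sample Size).

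- 53 × 3/4 = 39.75 and 53 × 1/4 = 13.25, or about 40 active and 13 placebo.
- Equal related-event rates: 40 / (40 + 13) = 75.5% of breaks fall in the active arms by allocation alone, with the same proportion unblinded in each.
- Assumed rate on cells twice that on placebo: 80 / (80 + 13) = 86%. Three times: 120 / (120 + 13) = 90%.

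Nothing in the documents says which of these applies.

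**6. Illustrative bias with no true effect.** Let p be the symptom rate, ra and rp the proportions unblinded on active and placebo, and d the relative change in reporting after unblinding. Suppose unblinded active participants report less and unblinded placebo participants report more:

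difference (active − placebo) = p(1 − ra·d) − p(1 + rp·d) = −p·d·(ra + rp)

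All inputs are assumptions.

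- Low end: p = 0.10, d = 0.25, ra = 0.10, rp = 0.05 gives −0.10 × 0.25 × 0.15 = −0.4 points.
- High end: p = 0.30, d = 0.50, ra = 0.60, rp = 0.20 gives −0.30 × 0.50 × 0.80 = −12 points.
- Equal proportions, ra = rp = 0.10, with p from 0.10 to 0.30 and d from 0.25 to 0.50: −0.5 to −3.0 points.

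Reversing the assumed behaviour reverses the sign. The formula treats everyone as unblinded from Week 0, so for given inputs it overstates the effect of later breaks. For scale, one changed report among 13 placebo participants moves that arm by 1/13 = 7.7 points.

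**The case against.** The strongest reply is that unblinding is gated. Planned Unblinding requires the medical monitor and DSMB, and the companion section speaks of need. A reader might infer from the broader sentence alone that any suspected-related event opens the code automatically. The documents do not support that; it is the worst reading of a gated and inconsistent rule. What survives is that the gate names no criterion other than suspected relatedness.

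A reader might also infer that the blind would be lost disproportionately on cells. The documents do not say so. The protocol reports earlier treatments as well tolerated and says infusion reactions have not been observed with this product. All arms receive five infusions with the same premedication. The 3:1 allocation explains a majority of breaks on active treatment without any difference in proportion. Equal proportions do not by themselves guarantee no bias, since knowing one received cells and knowing one received placebo may act differently, but that too is assumption.

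The endpoint is not purely self-reported. Fever has a 38 °C threshold in the objectives, temperature is taken at in-person visits, and symptomatic participants are asked to see a physician and be tested. Hospitalization, listed first among the primary endpoints, depends less on reporting. Even so, the pre-infusion symptom check is a telephone call, testing follows symptoms, and the documents do not define how the symptom endpoint is ascertained.

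Finally, SAP section 5.4 calls the testing exploratory, and the protocol describes the product's risks in this population as unknown, so wider disclosure after a related event has some argument behind it. These points lower the severity. They do not reconcile the two rules.

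**Conclusion.** The point holds as a conflict between two protocol sections, together with a gap in the SAP. That part needs no assumption. It also follows from the text that the broader rule could unblind participants and researchers with 12 to 26 weeks of symptom and SF-36 collection left after an infusion-related event, and that those completing five infusions would be analysed without any allowance for it.

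How much bias would follow cannot be determined. The 0.4 to 12 point range rests wholly on assumed symptom rates, unblinding proportions and changes in reporting, and its sign is not fixed. Whether the proportion unblinded would differ between arms is also unknown. Severity: should-fix.

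**What to change.** **Protocol.** Reconcile the two sections into one need-based code-break rule in line with Blinding for Clinical Evaluators, with one stated decision-maker. Suspected relatedness alone should not open the code to the participant or to efficacy evaluators. Disclosure should be limited to those who need the assignment. The DSMB can review by arm through the randomizer.

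**Log.** Record the date, reason, recipient and arm of every code break, and report them by arm.

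**SAP.** Pre-specify supportive analyses of the symptom endpoint, reported beside the primary result and not replacing it:

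- Kaplan-Meier time to first symptom (already planned in section 5.5), censored at code break. State that this censoring may be informative, because the break follows a suspected-related event.
- The binomial comparison repeated, counting only symptoms that began before any code break. A symptom that itself leads to a break counts as an event. State that this shortens observation for unblinded participants, so an arm with more or earlier breaks will show fewer events for that reason alone.

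**Cost.** Protocol and SAP wording, one log and two supportive analyses, with no added visits or patients. The small downside is that some participants with related events would learn their assignment only at study end.
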